10. TRIAL DESIGN

This pilot is an individually randomised, parallel group trial.

10.1. Inclusion and exclusion criteria

Inclusion criteria:

Women aged 15 to 30 years with a need for current or future contraception, attending one of the study sites, able to read English, with an active email account and access to the internet.

Exclusion criteria:

Women unable to provide informed consent (e.g. severe learning difficulties). Women needing a language advocate to understand English since the intervention content is intended to be accessed in private.

10.2. The Intervention

There are four main contents to the intervention. 1) General information on contraception, including information on each method as well as contraceptive benefits and side-effects and other common concerns. 2) Videos of women as well as health professionals discussing contraceptive experiences, concerns and misconceptions. 3) An interactive tool to help women chose a method of contraception which provides individually tailored results. 4) A page offering a link to NHS clinic finders as well as links to other useful resources, such as further information on sexual health, or websites offering support and advice for sexual abuse for example.

The website was based on evidence from the literature, qualitative interviews with men, and discussions with clinical and academic experts in sexual health. The development process was iterative, incorporating a high level of user involvement. The intervention is designed to be delivered initially in clinic, but also providing (and encouraging) access for the intervention group after patients have left clinic. This is to allow the intervention to be integrated into the clinic pathway, and also to take advantage of a 'teachable moment' when patients are engaged in thinking about their health, and so may be more amenable to behaviour change.¹⁵

The intervention comprises a website, displayed on a 'tablet' computer. Whilst in clinic, users allocated to the intervention group will be asked to work through a tailored package of individualised website content. After leaving clinic, the website will be available for them to re-visit and explore freely, and will be accessible on mobile phones as well as desktop computers.

Women randomised to the intervention group will be taken through a series of questions designed to identify appropriate method(s) that best suits individual preferences e.g. for a non-hormonal method, or one that does not require insertion by a health care professional, or one that is invisible, or one that can be forgotten about once inserted.

The website will give information to address women's concerns and barriers to uptake of LARC. A contraceptive choice tool will take account of women's views and preferences on the benefits and side effects of contraception and three suitable contraceptive options will be recommended with brief annotation, that can be emailed, texted to a mobile phone and used in a subsequent consultation and / or taken home.

Women randomised to the control group will be thanked for their participation and will then access standard contraceptive care only. All women in both intervention and control groups will be asked by automated email to complete the same outcome questionnaires online at 3 and 6 months (or 2 months post-partum). The control group will be offered access to the intervention website at the end of the study (after completion of 6 month follow-up).

10.3. Procedure

On arrival at each of the sites, female clinic users will be given a flyer about the trial by the reception or research staff. This will give very brief information about the study, indicating the inclusion criteria (See flyer). This information will also be available on posters within the waiting room and the clinic rooms (see poster). Flyers and posters will direct participants to the tablet computer in the waiting room, or suggest that they approach the researcher (trial manager) or research nurse, if they are available. Clinic staff will also be asked to talk to eligible patients about the research, give them a flyer with brief information (if they have not already received one), and refer them to a member of research staff or directly to the tablet device, if interested.

Where possible, recruitment will be self-directed, using a tablet computer (e.g., iPad), which will be available in the waiting room (this will be secured to prevent theft). The trial software will be set-up to allow participants to be taken through the steps of screening, consent, automatic randomisation, data collection, and intervention viewing, without assistance from the staff. The trial manager [name] or a member of clinic research staff will be present most of the time to assist and answer questions regarding trial registration only (not concerning clinical questions). When research staff are not available, a mobile number for the trial manager [name] will be provided for potential participants' questions. The online recruitment and consent procedures are based on those from two previous online trials conducted by members of the study team: the Sexunzipped online trial and the Men's Safer Sex online trial.^{16,17} In both of these studies, attracting participant interest was straightforward. Participants found the enrolment procedures and baseline questions onerous and time-consuming, and so we have streamlined the online trial software, and

minimised the number of questions asked at baseline and follow-up (see online trial software framework and outcome questionnaires). We will maximise follow-up rates by using three routes to contact participants (with participant permission): by email, mobile phone, and by post. Evidence suggests that online trials are an efficient method of conducting clinical trials of low-risk interventions, and such methods are acceptable to participants.¹⁸ Furthermore, online recruitment methods in trials of online interventions can improve the validity of the findings.¹⁹

The tablet device in the clinic waiting room will only allow patients to use the trial-related software and the intervention website (no other websites), and they will be led sequentially through the steps of recruitment and consent (see Figure 1). Initially, participants will be given some brief information about the trial and an invitation to participate. Then, they will be asked to complete a screening questionnaire to determine their eligibility for the trial^a. Those who are ineligible at this point will be informed of this, and thanked for their time. Those who are eligible will receive detailed information about the study^b. At this point, participants will be told that they can ask the research staff any questions regarding registering for the trial that they may have, and will be offered the mobile number of a member of research staff, in the case that none are available on site. If necessary, participants will be taken to a side room to discuss any queries regarding research participation. Participants will then be directed to a screen where they will give informed consent by agreeing to a number of statements (e.g., that we may contact them by email, mobile phone and post, that they understand what is involved, and that they agree to take part). Patients who do not consent (i.e., they do not agree to all the statements), will be informed that they cannot participate, and thanked for their time. Participants will be allowed a reasonable amount of time to decide whether they wish to consent, as they will be permitted to return to the tablet at any point during their clinic visit. However, as the intervention is designed to be integrated into the clinic journey, participants must sign up to the study before leaving the clinic.

Participants will then be asked to give their contact details (email address, telephone number, and postal address), in order to contact them for follow up assessments, to send the intervention group reminders to view the website, and to remind them that they are participating in the trial, and to send an electronic voucher to recompense participants for their time. Participants will be given the option not to give some of this information; however an email address is compulsory, to contact them for follow-up assessments. Participants who decline to give an email address will be excluded from the study.

^a This information will be completely anonymous, as participants will not be asked to give any personally identifying details. This data will only be stored for information regarding recruitment and exclusion ^b if they choose to participate, this will be sent to them via email for future reference

Demographic and baseline sexual health data will then be collected (see '*Measures*'). Participants will be given the option to withdraw from the study at any time after giving consent. All follow-up emails that participants receive will include a link to allow them to withdraw from the study, including one which will be sent to them immediately after registration.

Funder-approved amendment to recruitment

In addition to the recruitment above, we will recruit an additional 530 women from one site only, the Margaret Pyke Centre, via their Central online Booking System. Currently, when women request an appointment for contraception, they are directed to the Trust website to book their appointment. For this study, women will be informed on the Trust website that the clinic is taking part in a study to improve information about contraception, and inviting them to go online (by clicking on a hyperlink) and see if they want to take part in the study before they attend their appointment. Clicking on the hyperlink will take women to the trial website from where all procedures are the same as above.

It is routine practice at the Margaret Pyke Centre to send patients a text message to confirm their appointment. For this study, women who have booked a contraceptive appointment will be sent an additional text informing them that the clinic is taking part in a study to improve information about contraception, and inviting them to go online (by clicking on a hyperlink) and see if they want to take part in the study before they attend their appointment. Clicking on the hyperlink will take women to the trial website from where all procedures are the same as above.

Randomisation procedures

A randomisation list will be generated for the trial by a random number based algorithm in the computer software Stata. This list will be incorporated into the trial software programme before the trial begins, to allocate all participants to either the intervention or control condition. This allocation will be unalterable. Allocation will be concealed until the point of allocation, which will be immediate.

Participants allocated to the control condition will be notified that they have not been selected to view the intervention and told they will be contacted again in 3 and 6 months (or two months post-partum) to gather follow-up data. Those allocated to the intervention condition will be directed to the intervention website. Patients may stop viewing the website whenever they wish, and buttons will be included on the web pages to exit, recording whether they exiting because they want to (e.g., if they're bored), or if they are being called in to see the clinic staff. This data will be recorded, in order to give information about feasibility of website usage in practice.

For patients recruited through the MPC Central Booking Office there will be a variable interval of a few days before they attend their clinic appointment. All other registration and

intervention viewing is designed to take place in the waiting room, whilst patients are waiting to be seen by the clinic staff. This is designed to mimic how the intervention may work in practice – it can be offered to patients on arrival, so that they can complete activities in the time that they are waiting (often up to an hour).

At three and six months after their initial clinic visit, participants will receive an automated email requesting them to complete a follow-up questionnaire (see ', including a link to the online questionnaire (see Appendix, outcome questionnaires). If they do not complete the questionnaire, they will receive 4 further email prompts, at one-week intervals, and two text messages to their mobile phone (including the web link to the online questionnaire). If participants still do not respond, the researcher will telephone these participants, reminding them about the questionnaire and offering them the opportunity to complete it over the telephone. Finally, non-responders will be sent outcome questionnaires by post (once only).

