4. SUMMARY

Reducing unintended pregnancy is a national and global priority, and improving women's choice of contraception is a vital step. There are many myths, misunderstandings and concerns about contraception, and increasingly women turn to online resources for information on healthcare.

The aim of the study is to develop and test the feasibility of an online trial of a website to increase the acceptability, uptake and adherence to long-acting reversible contraceptive (LARC) methods in young women. LARC methods include the intrauterine device (IUD), intrauterine system (IUS), subdermal implant (SDI) and depo injection.

In Phase 1 of this study (completed) we developed a self-guided website that presents recommended contraceptive options in response to women's preferences. The website will be presented on a touch-screen tablet computer in clinic waiting areas or pharmacy consulting areas.

In Phase 2 (this study), we will assess feasibility of an online trial of the contraception choice website in five sites:

An NHS sexual health service (Margaret Pyke Centre, MPC)

A local general practice

A maternity service (Ashford & St Peter's Hospitals NHS Foundation Trust)

A community pharmacy (Greenlight)

An abortion service (bpas)

Phase Two will take 15 months including:

- Conducting a randomised pilot trial across the five settings
- Conducting a qualitative process evaluation of the website, of NHS implementation issues and of research procedures
- Analysis, reporting and dissemination of study findings
- Preparation of outputs, including a protocol for a definitive RCT to increase uptake and adherence of LARC that is informed by both quantitative and qualitative findings In each setting we will recruit 80 women aged 15-30 years (40 randomised to intervention and 40 to control) and follow them up by online questionnaire at 3 and 6 months (or 2 months after delivery for post-partum women).
- *Funder-approved amendment to recruitment*. In addition to the above, we will recruit 530 more women from one site only, the Margaret Pyke Centre, via their Central (telephone) Booking System. Women requesting an appointment for

contraception will be invited to go online and enter the trial before they attend their appointment.

Data collection:

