- Provider views about impacts on the service and trial procedures, assessed through qualitative interviews with 15 key staff in total (3 per site), sampling those who have roles in facilitating the study in each setting (e.g. receptionists, practice managers, nurses, midwives, doctors and pharmacists) (see Topic Guide). Questions to be explored include:
 - Are recruitment procedures acceptable to staff?
 - How might recruitment procedures be improved, to optimise recruitment to a fullscale trial?
 - What are staff views on the feasibility and usefulness of a contraception decision website in each clinic setting?

9. SAMPLE SIZE and RECRUITMENT

The original target sample size of 80 participants in each of the five settings was based on estimating an expected follow-up rate at 6 months of 70% to within 10% precision (95% Cl 60% to 80%) for each setting. This sample size also provided 80% power to detect a significant difference (at the 5% level) in the follow-up rate between two settings if the true difference is 22% (e.g. 59% vs. 81%). By pooling data across settings this sample size also provides 80% power to detect a significant difference (at the 5% level) in the follow-up rate between the follow-up rate between the intervention and standard arms if the true difference is 15% (e.g. 62.5% vs. 77.5%). The expected follow-up rate is based on a previous sexual health study that recruited and followed-up the participants online (Sex Unzipped).

Funder-approved amendment to sample size:

A further 530 participants are to be recruited from one existing site, though recruited in a different way (from the central booking system). Together with the original target size this

leads to a total of 930 participants. This new total sample size is calculated to provide power to assess the effect of the intervention on the revised primary outcome which is uptake of LARC at follow-up. Specifically, assuming a follow-up rate of 70%, this sample size provides at 82% power to detect as significant (at the 5% level) an increase from 35% (control group prevalence) to 47% in LARC use due to the intervention.

The recruitment period of 6 months is based on:

- the volume of patients attending each of the study sites, which is high i.e. hundreds or dozens of women per week in four sites GP, SRH, maternity service and bpasand at least 30 women per month in the pharmacy,

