The primary outcome of LARC use at 6 months will be analysed among women in need of contraception (not pregnant or currently trying to become pregnant) and the primary outcome of satisfaction with method will be analysed among women who are using a method at 6 months. The primary outcome of LARC use at 6 months will be analysed stratified by LARC use at baseline, leading to three intervention effects: the effect in baseline LARC users, the effect in baseline non-users, and the overall effect adjusted for baseline LARC use. In the event that over 90% of baseline LARC users in the control arm are using a LARC method at 6 months (or no longer need contraception) then the primary effect measure for this outcome will be the intervention effect in non-LARC users. If conversely fewer than 90% of baseline LARC users in the control arm are using a LARC method at 6 months then the primary effect measure will be the overall adjusted intervention effect. A further subgroup analysis will be conducted for both primary outcomes to assess, based on testing an interaction term, whether the effect of the intervention varies by setting.

Primary comparisons between arms will be based on multiple imputation where outcomes at 6 months are imputed based on outcomes at 3 months for those participants who completed the 3 month outcome questionnaire but failed to complete the questionnaire at 6 months.

Health Economics

The primary analysis will be a budget impact analysis of the website and contraception reporting the total costs to each payer (NHS (primary care versus secondary care), local government, private and out of pocket). This will reported as total cost of contraception and pregnancy outcomes for a range of different population sizes. The analysis will conform to the ISPOR good practice guidelines for budget impact analysis.²¹

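### The protocol states 40:40 in each setting but describes one list with no balancing by setting, and the stated adjustment of the primary LARC effect leaves out setting and recruitment route

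*Protocol*

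**What the plan says.** Section 4 (Summary) fixes the split by setting: "In each setting we will recruit 80 women aged 15-30 years (40 randomised to intervention and 40 to control". The funder-approved amendment then adds a large group from one clinic: "we will recruit 530 more women from one site only, the Margaret Pyke Centre". Section 9 says this "leads to a total of 930 participants".

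Section 10 gives the unit of allocation: "This pilot is an individually randomised, parallel group trial". The randomisation text within Section 10.3 says: "A randomisation list will be generated for the trial by a random number based algorithm in the computer software Stata". It continues: "This list will be incorporated into the trial software programme before the trial begins, to allocate all participants". Blocks, strata, minimisation and setting-specific lists are not mentioned there or elsewhere in the protocol.

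The same section separates the booking-system women from the rest by timing: "For patients recruited through the MPC Central Booking Office there will be a variable interval of a few days". All other women register and view the website in the waiting room.

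Section 10.5 promises adjusted effect measures without a general covariate list. For LARC use at 6 months it names three effects: in baseline LARC users, in baseline non-users, and "the overall effect adjusted for baseline LARC use". Setting enters as a subgroup interaction test for both primary outcomes. Recruitment route does not appear in the analysis text. Section 10.11 leaves a data analysis plan to be agreed before the database is locked.

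**The concern.** Two things do not fit together.

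First, the Summary states a result of allocation (40:40 in every setting) and Section 10.3 describes no mechanism that produces it. A later analysis plan cannot repair this, because the list will already have been used.

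Second, the amendment changed who is in the trial, but the stated adjustment does not reflect the change. One clinic now supplies about two thirds of the women, most of them by a route in which randomisation and first viewing come before the visit. Section 10.2 presents delivery in clinic as a deliberate feature of the intervention, so timing is a real difference in delivery. Section 6 also gives reason to expect LARC use to differ by setting: it reports that many general practices can fit few or no LARC methods, and that pharmacies cannot supply the emergency IUD.

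At stake are the stated split, some precision in the primary LARC comparison, and a readable interaction test. If the booking-system women were counted with their clinic's waiting-room women, the largest cell of that test would mix two modes of delivery.

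**Working it through.** **Make-up of the sample (Sections 4 and 9).**
- Total: 5 × 80 + 530 = 930, which reproduces the protocol's figure.
- Share from one clinic: (80 + 530)/930 = 610/930 = 65.6%.
- Share by the booking route: 530/930 = 57.0%.

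**Chance of the stated split.** Assumption: simple 1:1 allocation. The number X allocated to one arm in a setting of 80 is then Binomial(80, 0.5).
- P(X = 40) = C(80,40)/2^80 = 0.089.
- All five settings exactly 40:40: 0.0889^5 = 5.6 × 10⁻⁶.
- P(35:45 or worse) = 2 × P(X ≤ 35) = 0.314.
- At least one of five settings at 35:45 or worse: 1 − (1 − 0.314)^5 = 0.85.
- SD of X = √80/2 = 4.5; the 95% range is 31 to 49.

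Alternative assumption: one list balanced overall but not by setting (hypergeometric).
- P(40:40) = 9.3% if 80 are drawn from a balanced 930.
- P(40:40) = 9.9% if 80 are drawn from a balanced 400.

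So either unstratified reading gives about 9% to 10% per setting.

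**Cost in power.** Inputs from Section 9: 35% against 47%, 70% follow-up (930 × 0.70 = 651), 5% level, taken as two-sided. Pooled normal approximation:

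Power = Φ{[0.12 − 1.96 √(p̄(1 − p̄)(1/n₁ + 1/n₂))] / √(p₁(1 − p₁)/n₁ + p₂(1 − p₂)/n₂)}

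- Equal arms, 325.5 each: (0.12 − 0.0756)/0.0383 = 1.16, giving 87.7%.
- Arms of 435:495 randomised, the edge of the 95% range for 930 under simple randomisation: 87.6%.
- Difference: about 0.1 point.

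The protocol quotes 82% for these inputs. That gap is a separate matter; only the difference between the two rows is used here.

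Within one setting, 35:45 keeps 4 × 35 × 45/80² = 98% of the efficiency of 40:40.

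**Chance difference in setting mix between arms.** The protocol gives no LARC rates by setting, so these two sets are assumptions:
- Set A: 40% at the main clinic by both routes; 20%, 20%, 30% and 20% in the other four settings.
- Set B: 45% at the main clinic by both routes; 10%, 10%, 25% and 10% elsewhere.

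Under simple randomisation, the shift in the LARC difference caused by unequal mix has SD ≈ (2/N) √Σ nᵢ(pᵢ − p̄)².
- Set A (p̄ = 0.340): (2/930) × √7.03 = 0.57 points; 95% within 1.1 points.
- Set B (p̄ = 0.342): (2/930) × √21.85 = 1.0 points; 95% within 2.0 points.

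Among the 651 followed up, these SDs grow by √(930/651) = 1.20, to about 0.7 and 1.2 points. The target difference is 12 points.

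**The case against.** The strongest reply has five parts.

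- **The scheme is not stated to be simple.** The text names a generator and does not exclude blocks or setting-specific sections. This stands. A reader might infer that 40:40 cannot occur; the document does not support that, and even simple randomisation yields it about 9% of the time per setting. What remains is that no mechanism for the stated split is described.
- **40:40 may be only a nominal 1:1 target.** Section 8 speaks of up to 80 women per site, so even the 80 is loose. This is a fair reading, and if it is the intended one the Summary should say so.
- **Covariate lists are commonly left to the analysis plan.** This also stands in part: adjusted effects are promised without a full list, so omitting setting is not a proven error. But Section 10.5 does specify the adjustment of the overall LARC effect, and improving that specification is a fair recommendation. Nor is setting ignored, since it is tested as an interaction.
- **The interaction test may not merge the two routes.** The protocol does not say how booking-system women are classed. A reader might assume they are counted with their clinic; that is not stated, only left open.
- **The consequence is small.** This stands. A reader might infer that chance imbalance biases the trial, but with individual allocation it does not do so in expectation. A specific saving in sample size cannot be claimed either. It would rest on assumed rates, and it would overlap with the adjustment for baseline LARC use already planned.

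**Conclusion.** The point holds as an inconsistency and a cheap improvement. It does not threaten validity. The protocol states 40:40 in each setting and describes no step that delivers it; if the list is unstratified, the chance is about 9% per setting. The stated adjustment of the overall LARC effect omits setting and route. Both should be known for every woman and are plausibly prognostic, and 57% of the sample comes by a route with different timing of delivery.

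The size is modest: about 0.1 point of power from unequal arms, and a chance shift with an SD of 0.6 to 1.0 points (0.7 to 1.2 among those followed up) against a 12-point target. These figures assume simple randomisation, and the shift also assumes the two listed sets of setting rates. The gain in precision from adjusting depends on rates the protocol does not give, so no figure is put on it.

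**What to change.** 1. **Analysis.** Define one six-level factor: the five waiting-room settings, plus booking-system recruitment as its own level. Include it with baseline LARC use in the models for both primary outcomes. Use the same factor in the interaction test, so that pre-visit and same-day delivery are not mixed. For rare secondary outcomes such as pregnancy and STI, collapse or omit the factor: with 70% follow-up each 80-woman setting leaves about 56 women, and sparse events could make the model unstable.

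2. **Allocation.** State the method. For women not yet randomised, use randomly sized permuted blocks within setting/route. Do not cross these with baseline LARC use: that would make 12 strata, some probably almost empty. Because allocation is automated and concealed until the moment it is made, such blocks add little predictability. If the list is not changed, restate 40:40 in the Summary as a nominal 1:1 target.

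**Cost.** The analysis change needs a line or two of wording and five extra parameters per primary model. The allocation change needs a revised list in the trial software, which Section 10.3 says is loaded before the trial begins. The protocol does not show how many women remain to be randomised.

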8. OUTCOMES

Funder-approved Amendment to outcomes measures: (this effectively converts the secondary outcomes related to contraception into primary outcomes)

Primary Outcomes

- LARC method in use at 6 months measured by response to study outcome questionnaire
- Satisfaction with any chosen method of contraception at 6 months measured by response to study outcome questionnaire using a Likert scale 1-5. *How satisfied are you with the contraception you are using currently?*

Secondary Quantitative Outcomes

- Follow-up rate at 6 months after randomisation
- Recruitment rate measured via the trial website as the time taken to recruit (up to 80) women in each site. Recruitment is assessed by completing (in full or in part) the baseline questionnaire.
- Effectiveness of contraceptive method in use at 6 months measured by response to study outcome questionnaire and grouped as follows from least to most effective: no method; withdrawal or natural method; condoms or diaphragm; pill, patch or ring; LARC or sterilisation
- Change in method between baseline and 6 months, indicating whether any change is to a method of greater, lesser or similar effectiveness (based on grouping above)
- Pregnancy by 6 months measured at 3 months and at 6 months by response to study outcome questionnaire
- Sexually transmitted infection diagnosis by 6 months measured at 3 months and 6 months by response to study outcome questionnaire.

Health service and out-of-pocket costs for contraception and other sexual health services - measured at 3 months and at 6 months by response to study outcome questionnaire

Secondary Outcomes – qualitative

- Patient views and experience of the intervention and trial procedures, assessed through qualitative interviews at 2 weeks after randomisation with five women at each study site (total 25 interviews) (See Topic Guide). Questions to be explored include:
 - Are the online trial procedures acceptable to participants? E.g. the process of online registration and consent, the receipt of incentives, completing online questionnaires, contact and follow up by email and text
 - What are women's views of the intervention?
 - How might trial procedures be improved, to optimise retention in a full-scale trial?

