20. PROJECT TIMETABLE AND MILESTONES

Project Timetable

Phase 2 Feasibility	Month 1	Month 2	Month 3	Month 4	Month 5	Month 6	Month 7	Month 8	Month 9	Month 10	Month 11	Month 12	Month 13	Month 14	Month 15
	Jul17	Aug17	Sep17	Oct17	Nov17	Dec17	Jan18	Feb18	Mar18	Apr18	May18	Jun18	Jul18	Aug18	Sep18
Advisory Group Meeting															
Steering Committee Meeting															
Feasibility trial recruitment (80 women in each setting)															
Online follow-up at 3 months post-randomisation															
Online follow-up at 6 months post-randomisation															
Process (qualitative) evaluation															
Analysis of qualitative and quantitative date including health economics															
Dissemination of findings and final report															

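### Section 10.3 starts the follow-up clock at the first clinic visit and sections 8 and 20 start it at randomisation, so a booking-route woman who never attends has a follow-up date under one rule and not the other

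*Protocol*

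**What the plan says.** The contact procedure, near the end of section 10.3, reads: "At three and six months after their initial clinic visit, participants will receive an automated email". The reminder emails, texts, telephone call and postal questionnaire all follow from non-response to that first email.

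Other places use a different origin or none:

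- Section 8 defines a secondary outcome as "Follow-up rate at 6 months after randomisation".
- The section 20 timetable has rows for "Online follow-up at 3 months post-randomisation" and "Online follow-up at 6 months post-randomisation".
- Section 10.3 says that women allocated to control are "told they will be contacted again in 3 and 6 months (or two months post-partum) to gather follow-up data", which is naturally counted from allocation.
- Section 10.2 says that every woman in both arms will be asked by automated email to complete the questionnaires at 3 and 6 months, or 2 months post-partum. It sets no condition about attendance.
- The primary outcome, "LARC method in use at 6 months measured by response to study outcome questionnaire", names no origin.

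Under the recruitment amendment in section 10.3, 530 extra women from one site are invited to go online and "see if they want to take part in the study before they attend their appointment". Allocation is immediate on registration. For these women "there will be a variable interval of a few days before they attend their clinic appointment".

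**The concern.** In the original design, registration, randomisation and the visit took place on one occasion in the waiting room, so it made no difference which event started the clock. The amendment separates them for most of the sample, and the sentence that triggers the emails still refers to the visit.

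Two things follow if that sentence is applied as written. A woman who registers through the booking route and then does not attend has no trigger date. And time zero is set by an event that happens after randomisation. Intervention women see the website before the appointment, so it could affect whether or when they attend. Follow-up that depends on attendance would then select women on something the intervention may have changed. The sentence also gives the software vendor a different rule from the one in the outcomes section and the timetable.

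**Working it through.** **1. The stated origins side by side**

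| Place in protocol | Follow-up counted from |
|---|---|
| Section 10.3, email trigger | initial clinic visit |
| Section 8, follow-up rate | randomisation |
| Section 20, 3-month row | randomisation |
| Section 20, 6-month row | randomisation |
| Section 10.3, what controls are told | allocation, by implication |
| Section 10.2, all women emailed | no origin, no attendance condition |
| Section 8, LARC use | no origin |

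The first row conflicts with the next three, and the primary outcome does not settle the matter.

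**2. Who is affected**

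In the waiting-room route, visit and randomisation coincide and there is no difference. In the booking route they do not. Its share of the sample is 530 / 930 = 57.0%.

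**3. Booking-route women who attend**

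The protocol puts the gap at a few days. Assuming 3 to 14 days against six months of about 182.6 days: 3 / 182.6 = 1.6% and 14 / 182.6 = 7.7%. This is minor.

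**4. Booking-route women who do not attend**

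Under sections 8 and 20 the date is six months after randomisation. Under the email trigger in section 10.3 it is undefined. If that trigger alone governed, the woman would return neither questionnaire. Section 10.5 restricts the primary analysis to women with at least one completed follow-up questionnaire, so she would fall outside it. The imputation in section 10.5 uses the 3-month response to fill in the 6-month outcome, so it could not recover her either.

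**5. Size under the literal reading**

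The protocol's own power figure comes first. Inputs from section 9: N = 930, 70% followed up, 35% against 47%, 5% level (taken as two-sided). Equal allocation is assumed throughout.

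n per arm = 930 × 0.70 / 2 = 325.5; mean proportion = 0.41

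Power = Φ{[0.12 − 1.96 × √(2 × 0.41 × 0.59 / 325.5)] / √[(0.35 × 0.65 + 0.47 × 0.53) / 325.5]} = Φ{(0.12 − 0.0756) / 0.0383} = Φ(1.16) = 87.7%

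The stated 82% is not reproduced. The unpooled version gives 88.0% and the continuity-corrected version 86.0%. That is a separate matter and has no bearing on the clock.

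The documents give no non-attendance rate. Let a fraction *a* of the 530 not attend and yield no outcome. The number analysed is (930 − 530*a*) × 0.70, and power follows from the same formula.

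| Assumed *a* | Women without a trigger date | Analysed | Power |
|---|---|---|---|
| 0% | 0 | 651 | 87.7% |
| 5% | about 26 | 632 | 86.8% |
| 10% | 53 | 614 | 85.8% |
| 20% | 106 | 577 | 83.6% |
| 30% | 159 | 540 | 81.1% |

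The table assumes that non-attenders would otherwise have responded at the average 70%. If they respond less often, less of the loss is due to the clock.

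**The case against.** The strongest reply is that the email trigger is leftover waiting-room wording and that the rest of the protocol shows the intent. Section 10.2 has all women in both arms emailed. Controls are told at allocation when they will be contacted. The contraception questionnaire in section 10.4 asks about methods used since enrolment. The emails are automated, and nothing describes the trial software recording an attendance date that could trigger them. The software does generate a randomisation date.

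Most of this stands. A reader might infer from section 10.3 that non-attenders have no date for the primary outcome and would never be sent a questionnaire. The documents do not support that as an unconditional statement: sections 8 and 20 give such women a date, and section 10.2 says they will be contacted.

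A reader might also infer that the primary analysis is confined to attenders and is biased by a calculable amount. No attenders-only analysis is planned; the set in section 10.5 is defined by questionnaire completion. Any bias figure would need attendance rates by arm and LARC use by attendance, and the documents give neither.

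What the reply does not remove is that the most specific statement of when the emails go out names a different event from the outcomes section and the timetable. No place says what happens to follow-up when a randomised woman misses her appointment.

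**Conclusion.** This is an internal inconsistency of minor severity. The two origins are both stated, they diverge for the route that supplies 57% of the sample, and for a woman in that route who never attends, one rule gives a follow-up date and the other does not.

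For attenders the effect is a few days and can be ignored. For non-attenders the size is unknown. About 26 to 159 women would be affected if 5% to 30% failed to attend and the visit-based trigger were followed literally; both conditions are assumptions. On the same basis, calculated power would fall from 87.7% to between 86.8% and 81.1%, dropping below the stated 82% only near the top of the range. The reason to correct the text is the possibility of selection after randomisation, together with an ambiguous instruction for whoever programs the emails. Power is not the main concern.

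**What to change.** In the contact procedure of section 10.3, replace the initial clinic visit with randomisation as the origin for the 3- and 6-month questionnaires, for both recruitment routes. Add, in line with section 10.2, that all randomised women are sent both questionnaires whether or not they attend. Keep the existing exception for post-partum women.

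The cost is one or two sentences. The randomisation date is generated at allocation, so no new data are needed, and the sample size and its power calculation do not change.
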